3.2 Aims and Objectives

The three specific aims will be realized in the context of the logic model shown in Fig. 3:

AIM 1: Assess the comparative effectiveness of two effective encounter decision aids (Option Grid and Picture Option Grid) against usual care on shared decision-making (SDM), decision quality, treatment choice and other direct outcomes in women, and differentially by socioeconomic status (SES).

Hypothesis 1. The encounter decision aids will increase SDM in the clinic visit and improve decision quality, knowledge, and quality of life in women of higher and lower SES compared to usual care. We also anticipate that they will reduce decision regret and improve the perceived integration of healthcare delivery (see Fig. 3).

Hypothesis 2. The Picture Option Grid will be more effective than the Option Grid at improving primary and secondary outcomes in women of lower SES. There will be no difference between the effects of the two encounter decision aids in women of higher SES.

AIM 2: Measure the effect of the Picture Option Grid on disparities in decision-making (decision quality, knowledge, and SDM) and treatment choice, and conduct an exploratory analysis of the mediation and moderation effects.

Hypothesis 1. Compared to the Option Grid and usual care arms, the Picture Option Grid will reduce disparities in decision quality, knowledge and participation in shared decision-making between women of lower and higher SES. It is also likely to reduce disparities in treatment choice.

Hypothesis 2. The effect of the Picture Option Grid on treatment choice will be mediated by post-intervention knowledge, shared decision-making, and post-intervention values (reported in 'What Matters Most to You' subscale of DQI, e.g., keeping breast, removing breast to gain peace of mind, avoiding radiation, etc.) (see Fig. 4).

[figure not shown]
Hypothesis 3. For women of lower SES, socioeconomic barriers (e.g., resource constraints, as reported in the Decision Quality Instrument) will affect treatment choice and thereby moderate the intervention's effect.

AIM 3: Explore strategies that promote the encounter decision aids' sustained use and dissemination using a theoretical implementation model.

Hypothesis 1. Pre-visit planning, minimal clinician training, flexibility of use, and integration into the workflow and EMR will facilitate sustained use.

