4.1.2 Randomized Controlled Superiority Trial (Aims 1 and 2)

According to Cooper et al., the most appropriate design for evaluating interventions that aim to eliminate disparities is a classic experimental design with random assignment to experimental and control groups, with measurements of key variables pre- and post-interventions⁸². We have thus chosen to conduct a three-arm, multi-site randomized controlled superiority trial with stratification by SES (high versus low) and randomization at the clinician level (nested within study sites) (see Fig. 5).

Fig. 5. CONSORT* Study Flow Diagram

*CONSORT stands for Consolidated Standards of Reporting Trials, as reported in the CONSORT statement⁸⁷.

At each site, we will use a cross-sectional study design and randomize participating clinicians (three to five clinicians per site) to one of three arms (Picture Option Grid, Option Grid, or usual

care). We will use an R script written by the study statistician to complete the surgeon randomization. At each site, patients who have given informed consent and are seeing one of the participating clinicians will be allocated to the clinician's corresponding arm (Picture Option Grid, Option Grid, or usual care). Approximately the same number of patients in each socioeconomic stratum will be allocated to each arm. We will monitor accrual within each arm for each socioeconomic stratum at each site to ensure that a similar number of patients in each socioeconomic stratum receive each treatment. The total number of patients recruited at each site will be allowed to vary.

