4.8 Analysis

4.8.1 Power Calculation

For Aim 1, hypothesis 1, we base the effect size estimation on published data from randomized controlled trials of decision aids for breast cancer surgery^{32,41,115,116}, suggesting that a reasonable effect size for DQI is 9.34, that the standard deviation between patients in the intervention arms compared to usual care is 12.00, and that a within-physician intra-class correlation (ICC) of 0.05 is reasonable. This ICC is justified because treatment varies within clinic, thereby allowing heterogeneity that occurs between physicians across centers to be blocked. We assume that four physicians will participate in the study at each of the four clinics (at least one assigned to each of the three trial arms at each center) and assume a patient attrition rate of 20%. Under these assumptions, a study of 1,100 participants (68.75 participants per physicians and 366.66 per treatment group) has power of greater than 99.8%

to reject the null hypothesis that the encounter decision aid groups and the control group have equal means, using a two-sided 0.05 level test when the true mean difference is 9.34. Given recruitment difficulties due to seasonal trends in breast cancer diagnoses and a lower number of eligible patients than planned based on the feasibility assessments (see reasons in modification letter), the sample size has been revised to 600 participants. The power will remain above 80% for all primary hypotheses.

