A crucial feature of this power calculation is that the design-effect equals 4.04, implying that approximately 4 times as many patients are needed to obtain the same power as for a study with patient-level randomization. Power remains above the traditional 80% threshold with an ICC greater than 0.19, implying that the power remains adequate even if the level of clustering of patients within physicians is greater than anticipated. Further, the attrition rate of 20% is expected to be an overestimate given the brevity of the trial. The standard deviation between patients' DQI values deliberately errs on the side of an overestimate; hence, power may be substantially greater. For hypothesis 2, we are basing the effect size estimation on the comparison between Picture Option Grid and Option Grid in women of lower SES. Because we anticipate obtaining a similar number of women in the higher and lower SES categories, the same power calculation is performed on a sample size of half the size. With 550 patients in total (34.375 patients on average per physician), under the same assumptions as above, the power for this subgroup test is 99% with ICC = 0.05 and 80% with ICC = 0.175.

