For Aim 2, the power of the test for disparities between higher and lower SES is necessarily lower than the overall test at the same effect size, as four groups are compared (Picture Option Grid higher SES, Picture Option Grid lower SES, Option Grid and usual care higher SES, Option Grid and usual care lower SES). However, because patient SES varies within physician, power can be conservatively computed as if the patient-level variance was doubled and the total number of patients halved. If the true difference in the effect of the Picture Option Grid on DQI between the higher and lower SES groups is 8.5 compared to Option Grid or compared to usual care, the power for a two-sided alpha-level test at the 0.05-level is just above 80%. With a revised sample size of 600 participants, the power is unlikely to reach 80%. However, given those power calculations are resting on assumptions that may not be entirely accurate, we will know once we start the analysis if we have enough power for aim 2 hypotheses with a sample size of 600 participants. A significant finding is even more likely to be obtained if the estimated variability in the data turns out to be much smaller than assumed here. It could indeed be the case with the revised sample size. It is not critical to account for multiple testing because in both the primary (Aim 1) and secondary (Aim 2) analyses, a single pair of groups is compared.

We are assuming an effect size of 9.34 based on past studies of decision aids for breast cancer surgery^{32,41,115}.

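### Aim 1 Hypothesis 2 predicts no difference between the two aids in higher-SES women, which the planned tests cannot establish, and its lower-SES power reuses the aid-versus-control effect of 9.34 at a sample size the trial no longer has

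*Combined protocol and SAP*

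**What the plan says.** **Hypothesis (3.2, Aim 1, Hypothesis 2).** For lower SES: "The Picture Option Grid will be more effective than the Option Grid at improving primary and secondary outcomes in women of lower SES". For higher SES: "There will be no difference between the effects of the two encounter decision aids in women of higher SES".

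**Framework (4.1.2).** The trial is a "three-arm, multi-site randomized controlled superiority trial with stratification by SES". No equivalence or non-inferiority margin appears anywhere, and no power is given for the higher-SES statement.

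**Analysis (4.8.3).** Each SES measure and its interaction with the intervention indicators enter the model. Non-significant interactions are removed. Otherwise the intervention effects are estimated by SES stratum.

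**Power (4.8.1).** For Hypothesis 1 the cited trials are read as "suggesting that a reasonable effect size for DQI is 9.34". The stated aim of the test is "to reject the null hypothesis that the encounter decision aid groups and the control group have equal means", so 9.34 describes the aid groups against control, tested at the two-sided 5% level. For Hypothesis 2 the text says the effect size comes from comparing the two aids in lower-SES women, but it states no value. It repeats the calculation on half the sample (550): "under the same assumptions as above, the power for this subgroup test is 99% with ICC = 0.05". At an ICC of 0.175 the stated power falls to 80%. The section closes: "We are assuming an effect size of 9.34 based on past studies of decision aids for breast cancer surgery".

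**Revised size.** Section 4.8.1 lowers the total to 600, and section 8.2.1 gives about 300 women in each SES group. The Hypothesis 2 power was not restated.

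**The concern.** There are two separate weaknesses in one hypothesis.

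1. A superiority or interaction test that misses significance shows that a difference was not detected. It does not show that the difference is nil. A significant interaction would show that the contrast between the aids varies with SES, but not that it is zero in higher-SES women. Without a margin or a confidence-interval rule, nothing in the plan can support the higher-SES half of the hypothesis.

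2. The effect used for aid versus aid is the one assumed for aid versus control. Section 3.1.2 says no study has compared a pictorial with a text-based encounter aid across socioeconomic strata. Section 4.4 describes two aids with the same medium and delivery mode and reading grades of 6.5 and 6.6, and section 4.4.2 says the Picture Option Grid uses the same evidence. A gap between them as large as the whole effect of an aid over usual care may be right, but it needs an argument, and none is given.

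Picture versus text by SES is the trial's distinctive question. Readers could be told the aids perform alike in higher-SES women when differences of several points remain compatible with the data. They could also take a null result in lower-SES women as coming from a test with 99% power.

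**Working it through.** **Inputs (4.8.1, 8.2.1).** Effect 9.34; SD 12; ICC 0.05 or 0.175; 4 × 4 = 16 physicians; attrition 20%; two-sided 0.05; three equal arms; 550 lower-SES women as stated, about 300 as revised.

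**Formulas.** Evaluable n per arm = 0.8N/3; m = 0.8N/16 per physician; DE = 1 + (m − 1) × ICC; SE = 12 × √(2 × DE / n per arm); power = Φ(effect/SE − 1.96).

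**Step 1: reproduce the plan's figures (N = 550).** n per arm = 146.67 and m = 27.5.
- ICC 0.05: DE = 1 + 26.5 × 0.05 = 2.325; SE = 2.137; 9.34/2.137 = 4.37; power 99.2% (stated 99%).
- ICC 0.175: DE = 5.637; SE = 3.327; 9.34/3.327 = 2.81; power 80.2% (stated 80%).

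Both match, so the aid-versus-aid power does use 9.34.

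**Step 2: the revised size (N = 300).** n per arm = 80 and m = 15.

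| | ICC 0.05 | ICC 0.175 |
|---|---|---|
| DE | 1.70 | 3.45 |
| SE | 2.474 | 3.524 |
| Power at 9.34 | 96.5% | 75.5% |
| Detectable at 80% power (2.80 × SE) | 6.9 | 9.9 |
| 95% CI half-width (1.96 × SE) | 4.85 | 6.91 |

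These use normal quantiles. Two arms hold about 16 × 2/3 = 10.67 physicians, so about 9 cluster degrees of freedom. On that basis power at 9.34 falls to about 92% (ICC 0.05) and 65% (ICC 0.175), half-widths rise to 5.6 and 8.0, and detectable differences are somewhat larger. The half-widths apply to either SES stratum, since each has about 300 women.

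**Step 3: smaller effects.** The documents give no Picture-versus-Option Grid effect, so these values are assumptions (N = 300, normal approximation).

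| Assumed effect | ICC 0.05 | ICC 0.175 |
|---|---|---|
| 4.67 (half of 9.34) | 47% | 26% |
| 3.11 (a third of 9.34) | 24% | 14% |

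**Step 4: what 9.34 between the aids implies in lower-SES women, taken with Hypothesis 1.**
- Option Grid no better than usual care: Picture is 9.34 above usual care (9.34/12 = 0.78 SD).
- The two aids average 9.34: Picture is 9.34 + 4.67 = 14.0 above (1.17 SD) and Option Grid 4.67.
- Option Grid itself gains 9.34: Picture is 18.7 above (1.56 SD).

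**The case against.** **The sentence is an expectation in the aims section, not a decision rule.** This largely stands. A reader might infer that the plan counts low precision in higher-SES women as confirmation, but no such rule is written. Section 4.8.3 allows stratified analyses only after a significant interaction, and low precision makes that less likely. What remains is that the prediction is stated flatly, while some neighbouring hypotheses are worded as anticipated or likely, and nothing bars a non-significant result from being reported as its confirmation.

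**The interaction test is already planned.** True, and the fix keeps it. What is missing is an estimate with its interval when the interaction is non-significant, because the term is then dropped and no stratum contrast is specified.

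**The power is correct on the plan's own inputs.** It is. A reader might infer an arithmetic error or an underpowered hypothesis. The stated figures reproduce, and at 300 women power at 9.34 stays above 80% at ICC 0.05, in line with the claim in 4.8.1 for the revised size. The weakness lies in where the effect comes from and in the outdated sample size.

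**The 18.7-point gap is not a necessary consequence.** Agreed: it is the top of a range that starts at about 9.3. The protocol's argument that text-based aids suit low-literacy women poorly points toward the lower part.

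**Conclusion.** The point holds on both halves, as a matter of wording and restated power. The higher-SES prediction cannot be established by the planned tests: at the revised size the data would leave roughly ±4.9 points (ICC 0.05) to ±6.9 points (ICC 0.175) around the estimate. The lower-SES power is computed correctly, but from a borrowed effect and for 550 women. At about 300 it is 96.5% or 75.5% at 9.34, with detectable differences of 6.9 or 9.9 points. The second ICC matters because the plan itself quotes 80% power at 0.175.

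These figures assume SD 12, 20% attrition, 16 physicians, equal arms and a normal approximation, with no multiplicity adjustment. Cluster degrees of freedom make them less favourable. The 4.67 and 3.11 effects are illustrations. The documents do not show that the true difference between the aids is below 9.34, and nothing here touches Hypothesis 1.

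**What to change.** 1. **Section 3.2.** Replace the higher-SES sentence with: *We expect the difference between the Picture Option Grid and the Option Grid to be smaller in women of higher SES than in women of lower SES.* In 4.8.3 add: *The Picture-versus-Option Grid difference in each SES stratum, and the arm-by-SES interaction, will be reported with 95% confidence intervals whether or not the interaction is significant. A non-significant result will not be reported as no difference.* Give the expected half-widths (about 4.9 points at ICC 0.05, 6.9 at ICC 0.175). Section 4.8.1 already concedes that the related Aim 2 SES contrast is unlikely to reach 80% power at 600, so an estimate with its interval is the realistic product.

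2. **Section 4.8.1, Hypothesis 2 power.** Restate for about 300 lower-SES women: at 9.34, 96.5% at ICC 0.05 (about 92% with 9 cluster degrees of freedom) and 75.5% at ICC 0.175. Give the differences detectable with 80% power, 6.9 and 9.9 points, and note that they are somewhat larger with cluster degrees of freedom.

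3. **Section 4.8.1, source of the effect.** Say that 9.34 is borrowed from aid-versus-control studies, and show power for smaller effects labelled as assumptions, for example 47% at 4.67 with ICC 0.05.

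The cost is text only; design and sample size are unchanged. The stated power becomes less favourable.

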4.5 Outcomes

We have chosen outcome measures that are patient-centered and relevant to our target population with our patient and stakeholder partners. To accommodate varying levels of literacy and health literacy of our target group and to comply with patient partners' advice, we will use validated short-form questionnaires whenever possible. All patient and stakeholder partners have deemed the chosen measures important and relevant, highlighting their impact on patients' lives in both the short-term (e.g., treatment choice, anxiety) and longer-term (e.g., quality of life, decision regret). Aside from the Observer OPTION⁵ scale¹⁰², all are patient-reported outcome (PRO) measures. All included scales and tests are validated and have been developed and tested with patients. The demographic questions and item assessing the amount of out-of-pocket expenses incurred by the participant over the past month have not been validated.

We will measure outcomes at baseline (T0), during the clinic visit (T1), immediately after the visit (T2), one week post-surgery or around the first post-operative visit (T3) and 12 weeks post-surgery or around the second post-operative visit (T4). For all participants who receive surgery before May 2018, we will also measure decision regret and financial toxicity one year post-surgery (T5).

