4.5.1 Primary Outcome Measure

The primary outcome measure (see Table 3) is the validated 16-item Decision Quality Instrument (DQI) for breast cancer (see Appendix C), which includes a knowledge subscale⁸⁹. The DQI, designed to be administered post-decision, will be assessed at T2 and T3. It aims to measure the extent to which patients are informed about their options, are involved in the decision-making process, and receive a surgery (mastectomy or BCS) aligned with their values, attitude towards risks, and preferences. It produces three scores: (1) knowledge, (2) concordance, and (3) decision process. Validation demonstrated good feasibility with minimal missing data and good 4-week retest reliability for both knowledge (ICC = 0.70) and concordance (ICC > 0.72). Discriminant validity was acceptable⁸⁹.

Table 3. Outcome Measures According to Data Collection Periods

	TIMEPOINT						
	-T0	T0 Baseline	T1 In-Visit	T2 Post- Visit	T3 1 wk PS*	T4 12 wks PS**	T5 1 yr PS
CONSENT AND ENROLLMENT							
Eligibility Screen	X						
Informed Consent	X						
Allocation (via surgeon confirmation)	X						
INTERVENTIONS							
Arm 1: Option Grid			X				
Arm 2: Picture Option Grid			X				
Arm 3: Usual Care			X				
OUTCOME MEASURES							
Rates of recruitment – documented and tracked in REDCap		X					
Discontinuation rates – documented and tracked in REDCap		X		X	X	X	X
Demographic data – 6 items, self-reported		X					
Health literacy – 1-item Chew's health literacy screening		X					
Decision quality (primary outcome measure) – validated 16-item DQI, subscale adapted for low SES				X	X		

Knowledge – validated 5-item DQI knowledge subscale		X		(X)	(X)		
Treatment intention – self-reported via DQI				(X)			
Treatment choice – obtained from medical records					X		
Quality of life – validated 6-item EQ-5D-5L		X				X	
Anxiety – validated 8-item PROMIS anxiety short form		X		X	X	X	
Shared decision-making (observed) – validated OPTION ⁵			X				
Shared decision-making (self-reported) – validated 3-item CollaboRATE				X			
Decision regret – validated 5-item decision regret scale					X	X	X
Integration of health care delivery – validated 4-item IntegRATE		X				X	
Financial toxicity – four items from validated COST measure and self-report of out-of-pocket medical expenses in the past month					X	X	X
Intervention's patterns of use – questions and photos of intervention				X	X		

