Mastectomy

Both options have similar costs.

It is best to know what is covered by your insurance and what your out of pocket costs may be. Don't hesitate to ask your care team about this. They will know who can answer your questions.

Early stage breast cancer: What's right for me?

Notes and questions

Now that you have looked at the Picture Option Grid, this page is for your notes, thoughts or any questions for you to discuss with your doctor.

1. Will it affect how long I live?

6. Will I need radiation in the breast?

2. Will cancer come back in the breast?

7. Will my lymph nodes be removed?

3. What is removed in the breast?

8. Will I need chemotherapy and lose my hair?

4. Will I need more than one surgery?

9. How much will it cost?

5. How long will it take me to recover?

Other questions/thoughts:

Early stage breast cancer: What's right for me?

Editors: [name], [name], [name], [name], [name], [name], [name]

Evidence document: <http://optiongrid.org/cpresources/grid/evidences/9.pdf?x=Z4wDlBhPB>

Publication date: 23 August 2017 Expiry date: 23 August 2019

ISBN: 978-0-9550975-6-0 License: CC BY-NC_ND 4.0 (International)

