13 APPENDIX C. DECISION QUALITY WORKSHEET

DECISION QUALITY WORKSHEET FOR BREAST CANCER SURGERY

Instructions

This survey has questions about what it is like for you to make decisions about surgery for your early stage breast cancer.

Please circle the number  or check the circle  to answer each item.

Your answers will tell us three important things:

1. What matters most to you?
2. How well are we doing our job of giving you information?
3. What do you talk about with your health care providers?

Thank you!

Here are some definitions of terms that appear in this survey:

Early stage breast cancer is breast cancer in stage I, IIA, IIB or IIIA. It means the cancer may have spread nearby to lymph nodes but not to other parts of the body.

Lymph nodes are small clusters of tissues that help defend the body from the spread of infections and cancer. The lymph nodes under the armpit are often checked to see whether breast cancer has spread.

Lumpectomy is surgery to remove only the breast tumor and a border of healthy tissue around it, saving the breast. Lumpectomy is also called breast conserving surgery.

Breast reconstruction is surgery to recreate a breast shape. The surgeon will use a breast implant, tissue from another part of your body (called flaps), or a combination.

Mastectomy is surgery to remove the entire breast.

Radiation therapy is the use of high-energy x-rays to kill cancer cells. Radiation is a local therapy used to kill cancer cells that may remain in the breast area after surgery.

Section 1: What Matters Most to You

This set of questions includes some reasons other women have given for choosing their breast cancer surgery. We are interested in what is important to you.

Please mark on a scale from 0 to 10, how important each of the following are to you as you are thinking about your decision about surgery.

How important is it to you to . . .

	Not at all important										Extremely important	
1.1. keep your breast?	0	1	2	3	4	5	6	7	8	9	10	
1.2. remove your entire breast to gain peace of mind?	0	1	2	3	4	5	6	7	8	9	10	
1.3. avoid having radiation?	0	1	2	3	4	5	6	7	8	9	10	
1.4. have reconstruction to make a breast shape?	0	1	2	3	4	5	6	7	8	9	10	
1.5. avoid more surgery?	0	1	2	3	4	5	6	7	8	9	10	
1.6. Is there anything else that is important to you that we have missed?												

1.7. At the moment, what option are you leaning towards to treat your early stage breast cancer?

- Lumpectomy only
- Lumpectomy and radiation
- Mastectomy

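### Aim 2 Hypothesis 3 takes its moderator from a DQI subscale first given after the decision aid is used, so the interaction cannot cleanly support a moderation claim

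*Combined protocol and SAP*

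**What the plan says.** - **The hypothesis.** Section 3.2, Aim 2 Hypothesis 3, says that for lower-SES women socioeconomic barriers are expected to act on the surgery decision: "e.g., resource constraints, as reported in the Decision Quality Instrument) will affect treatment choice", and so to act as moderators of the intervention. The Aim 2 statement and the Fig. 4 legend both call the moderation analysis exploratory.
- **A neighbouring hypothesis.** Hypothesis 2 of the same aim takes values measured after the intervention, from the DQI values subscale, as a mediator of the Picture Option Grid's effect on treatment choice.
- **Timing.** Section 4.5 orders the assessments "during the clinic visit (T1), immediately after the visit (T2". Section 4.5.1 states: "The DQI, designed to be administered post-decision, will be assessed at T2 and T3". The only part of the DQI given at T0 is listed in Table 3 as "Knowledge – validated 5-item DQI knowledge subscale". Table 3 places the COST items and the out-of-pocket question at T3, T4 and T5.
- **Content.** Appendix C rates five values: keeping the breast, removing it, radiation, reconstruction and further surgery. Item 1.6 then asks, as free text, "Is there anything else that is important to you that we have missed". Section 4.1.4 plans to adapt this subscale to pick up barriers that matter to lower-SES women, and Table 3 describes the trial instrument as adapted.
- **The aids.** Row 9 of the Picture Option Grid (Appendix B) is about cost and says "Both options have similar costs". The Option Grid (Appendix A) has no cost row.
- **Analysis.** The aim statement in Section 4.8.4 mentions moderation, but the text describes only the SES disparity test and mediation. The interaction covariates in Section 4.8.8 are SES, age, ethnicity, race, literacy, language and site.

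**The concern.** A moderator should be fixed before treatment, so that women with and without it can be compared across arms on the same footing. If it is recorded afterwards and the arm can change what is reported, the women who report a barrier in one arm may differ in kind from those who report it in another. The interaction then mixes two things: a difference in the aid's effect, and a difference in who was led to report the barrier.

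At stake is one numbered, exploratory hypothesis, but it is the plan's route to a question that Section 3.1.2 leaves open: whether financial pressure, transport, childcare or the need to return to work shapes surgery choice regardless of knowledge and participation. With Appendix C as printed, the answer would rest on what some women volunteer in one free-text box after the visit.

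**Working it through.** No power or alpha figure is given for this hypothesis, so the check is a count of items and a comparison of sections.

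**1. Item counts.** Table 4's totals reproduce from its own rows with a 16-item DQI:
- T0: 1 + 6 + 5 + 6 + 8 + 4 = 30
- T2: 16 + 8 + 3 = 27
- T3: 16 + 8 + 5 + 5 = 34
- T4: 6 + 8 + 5 + 4 + 5 = 28
- T5: 5 + 5 = 10

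Appendix C has 7 + 5 + 7 = 19 numbered items. Without the free-text item 1.6 there are 18, and without the leaning question 1.7 as well there are 17. None of these equals 16. Of the 18 closed items, 0 ask about money, insurance, work, transport or childcare.

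**2. Order of events.**

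| Variable | First measured | Relative to use of the aid (T1) |
|---|---|---|
| Insurance | Screening | Before |
| Income, education | T0 | Before, for most women |
| DQI values subscale, item 1.6 | T2 | After |
| COST items, out-of-pocket expenses | T3 | After the aid and after surgery |

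The values subscale has no baseline administration. The exception to the first two data rows is in Section 4.7.4. Women unaware of their diagnosis before the consultation, and women who ask to enroll afterwards, complete T0 together with T2 after the visit.

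**3. Causal role.** Write A for arm, B for the reported barrier and Y for surgery choice:

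logit P(Y = 1) = α + β₁A + β₂B + β₃(A × B)

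Reading β₃ as moderation requires that B is not altered by A. Hypothesis 2 assumes that values from the same subscale are altered by A, since that is what makes them mediators. The plan gives no reason why an answer to item 1.6 on that page should be exempt.

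**4. A route from arm to report.** The Picture Option Grid raises cost; the Option Grid does not. The cost-discussions analysis in Section 4.8.6 sets out to test whether that row changes cost conversations. The protocol therefore treats an effect of arm on cost talk as a live possibility, and a T2 report of cost concerns comes straight after that talk.

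**5. What is available beforehand.** Section 4.8.3 already plans a poverty-income ratio, and Section 4.3.5 collects insurance at screening. Neither is plausibly changed by one consultation. Their range is narrow where Hypothesis 3 applies. Under the two-criterion definition in Section 3.1.1, lower-SES women are at or below 138% of the poverty level, so the ratio runs from 0 to about 1.38. If women are kept in the stratum on insurance alone, the range is wider.

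**The case against.** The strongest reply is that the subscale was to be adapted precisely to capture barriers (Section 4.1.4), and that Table 3 calls the instrument adapted. A reader might infer from Appendix C that the trial's DQI has no resource item at all. The documents do not support that, because they never say whether Appendix C is the adapted form. The adaptation milestone in Table 5 (6/30/17) predates the revision to 600 patients, and 19 items exceed 16, so it may be; that remains inference. This point stands, and the finding on content is limited to the appended version. It does not touch timing: adapted or not, the subscale is not given at T0.

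A reader might also infer that the hypothesis cannot be tested. That goes too far. Resource constraints are only an example of the barriers meant, baseline SES measures exist, SES-by-arm interactions are planned in Section 4.8.3, and a model with a T2 variable can be fitted because T2 precedes surgery. What fails is the interpretation of that model as moderation.

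It is also fair to say that bias is conditional. It arises only if the arm changes the report. That is plausible for cost. The documents give no reason to expect a transport, childcare or work constraint to change during one visit. Nor do they show that free-text answers would be missing differently by literacy or arm; staff read the questions to women who cannot read or write (Section 4.7.4).

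Finally, income and insurance help define the lower-SES stratum, so they are weak moderators within it. That is correct and is carried into the fix as a limitation.

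**Conclusion.** The concern holds in a limited form. The source named for the Hypothesis 3 moderator is first measured after the intervention, the appended version offers one free-text item and no closed item for it, and COST comes later still. An arm-by-barrier interaction on these responses cannot cleanly support a moderation claim. In addition, Section 4.8.4 gives no model for this hypothesis.

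The size of any bias cannot be computed: the documents give neither the frequency of reported constraints nor the effect of arm on reporting. The consequence is confined to an exploratory hypothesis in roughly 300 lower-SES women (Section 8.2.1), or about 300 / 3 = 100 per arm if accrual is balanced. The primary outcome and Aim 1 do not depend on it.

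The conclusion assumes that the values subscale is given on the schedule in Table 3 and that the Picture Option Grid's cost row is used in the visit. It does not depend on whether Appendix C is the adapted form.

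**What to change.** 1. In Sections 3.2 and 4.8.4, define the Hypothesis 3 moderator from pre-consultation data already collected: the continuous poverty-income ratio first, with insurance category as a secondary proxy. This assumes household size is recorded, as the ratio in Section 4.8.3 requires.
2. Specify the model: logistic regression of treatment choice on arm, moderator and their interaction, in lower-SES women, with the clustering by clinician that Section 4.8.3 already provides for.
3. Restrict the analysis to women whose T0 was completed before the consultation, or run that restriction as a sensitivity analysis.
4. Report any analysis by T2/T3 DQI responses or T3 COST responses as descriptive, not as moderation.
5. State whether Appendix C is the adapted instrument, and reconcile its 19 items with the stated 16.

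The cost is protocol and analysis-plan wording, with no new data. The price in information is real: the proxies have restricted range within the stratum and do not measure childcare, transport or work barriers, so a null interaction should not be read as showing that barriers are unimportant.

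As an option, the four COST items and the out-of-pocket question could be added at T0 for women still to be enrolled. That takes T0 from 30 to 35 items, against 34 already accepted at T3. The moderator would be missing for earlier enrollees, and for women who complete T0 after the consultation it would still be post-intervention.
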